4.7.8 Blood Collection - Biomarkers, Metabolomics, and Flow Cytometry:

Research blood samples will be collected at baseline, day 21, month 3 and 1 year post-transplant and will include no more than 16ml of blood per collection event (two NaH green top + one EDTA purple top) or 128ml (about 2 fluid ounces) in an 8-week period.

Subjects may be consented to multiple studies that contain the same research blood collection and analysis (specifically Pro00051024, Pro00089697, Pro00092963). If this situation occurs, duplicate research blood samples will not be collected. Instead, data derived from either Pro00051024 or Pro00089697 may be transferred to this study for analysis and reporting purposes.

Research blood samples will be processed as follows prior to biomarker, metabolomics, and flow cytometry analysis:

For Biomarker and Metabolomics analysis:

1. Draw one 4ml lavender top (K₂EDTA) tube.
2. Invert tube 10 times to mix blood.
3. Centrifuge at 4°C at 2500 x g for 15 minutes.
4. Remove plasma from tube and transfer into sterile 15ml conical tube.
5. Repeat centrifuge at 4°C at 2500 x g for 15 minutes.
6. Aliquot ≥1.0ml of plasma equally into 2.0ml cryovials, one for metabolomics, one for plasma biomarkers
7. Freeze at -80°C.

For Flow Cytometry analysis:

1. Draw two green top (Sodium Heparin) tubes.
2. Dilute sample with phosphate-buffered saline (PBS) at a ratio of 1:1.
3. Ficoll sample in accordance with laboratory SOP.
4. For every 1mL of PBMCs (peripheral blood mononuclear cell) collected add 100 µL DMSO (dimethyl sulfoxide).
5. Immediately freeze sample at -80°C.

Metabolomics

Approximately 1ml of plasma from the EDTA tube will be used for metabolomics analysis.

A Research Program Targeting Pre-, Peri-, and Post-transplant Optimization Program (R-POP)

Version 1.18: October 25, 2022

Targeted metabolomics: acylcarnitines and amino acids are analyzed using stable-isotope-dilution techniques. Measurements are made by flow-injection, tandem mass spectrometry, using serum or plasma sample preparation methods described previously (57, 58). Data are acquired using a triple-quadrupole detector equipped with an Acquity ultra-high-pressure liquid-chromatography system and controlled by the MassLynx 4.1 software platform, all from the Waters Corporation (Milford, MA).

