Whole blood samples, will be analyzed and monitored for outcomes such as immune cell differentiation, immune response and development of GVHD. Flow cytometry will be performed -b(7). Briefly, whole blood will be used for isolation of about 1×10^6 mononuclear cells. The mononuclear cells will be incubated with titrated antibodies for 15 minutes at room temperature in the dark. mononuclear cells will be lysed with FACS lysing solution (BD Biosciences, San Jose, CA). Cells will be stained with appropriate antibody cocktail and then analyzed using a FACScanto flow cytometer equipped with FACSDiva software (BD Biosciences). Absolute cells counts will be determined using a Flow-Count Fluorospheres (Beckman Coulter, Brea, CA). Examples of antibodies include: FITC-conjugated anti-CD62L (clone MEL-14), R-PE-conjugated anti-CD45.1 (clone A20), cy-chrome-conjugated anti-CD44 (clone IM7), and their isotype controls (all from BD PharMingen); and FITC-conjugated anti-H-2Db (clone CTDb), PE-conjugated anti-CD4 (clone CT-CD4), B220 (clone RA3-6B2), PE-Texas red-conjugated anti-CD4 (clone RM4-5), tricolor-conjugated anti-CD4 (clone CT-CD4), CD8 α (clone CT-CD8 α), and their isotype controls (Invitrogen, Carlsbad, CA).

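### Section 4.7.8: the bead-based absolute cell counts have no blood-volume denominator, and the two descriptions of the flow sample conflict

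*Combined protocol and SAP*

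**What the plan says.** Both descriptions are in protocol Section 4.7.8.

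**Processing list.** It opens with "Research blood samples will be processed as follows prior to biomarker, metabolomics, and flow cytometry analysis", so the steps precede the assay. For flow cytometry, two sodium heparin tubes are drawn. The steps are then "Dilute sample with phosphate-buffered saline (PBS) at a ratio of 1:1", "Ficoll sample in accordance with laboratory SOP", addition of DMSO in proportion to the volume of separated cells, and "Immediately freeze sample at -80°C". No step sets aside unseparated blood, records the volume processed, or counts the cells recovered.

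**Flow Cytometry subsection.** It introduces the material as whole blood and continues: "Briefly, whole blood will be used for isolation of about 1×10^6 mononuclear cells". Those cells are incubated with antibody, treated with a lysing solution, stained and run on the cytometer. Then: "Absolute cells counts will be determined using a Flow-Count Fluorospheres". The text does not say at which step, or into which material, the beads go. It gives no unit for the count.

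The outcomes named there are immune cell differentiation, immune response and development of GVHD. Section 6.0 has no analysis of absolute cell counts.

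**The concern.** A counting bead measures the number or concentration of cells in the tube to which it is added. Turning that into cells per microlitre of the patient's blood requires a known volume of blood behind the tube, and either no cell loss on the way or a measured loss. The processing list provides neither. It separates and freezes the cells, and both steps lose an unrecorded share of them.

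Samples are drawn repeatedly from baseline to 1 year, so comparison over time is the natural use. A result labelled absolute is likely to be taken as cells/µL of blood. A change between visits could then reflect how many cells were put in the tube, or how many survived the thaw, and not how many were circulating. Volume, yield and recovery cannot be reconstructed later if nobody records them.

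**Working it through.** The plan states no blood count, yield or conversion, so there is no figure to reproduce. The check is a mass balance.

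**Inputs from Section 4.7.8**
- Blood per draw: at most 16 mL, of which 4 mL is the EDTA tube. Heparin blood for flow is at most 16 − 4 = 12 mL.
- Cells isolated for the assay: about 1×10^6 mononuclear cells.

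**Assumptions (not in the documents)**
- Mononuclear count c: 100 to 2000/µL.
- Combined recovery r after separation and thaw: 30% to 90%, with 50% to 80% as a narrower range.
- CD4 share s: 20%, held constant.

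**What the beads measure.** Cells in tube = (cell events ÷ bead events) × beads added. The patient's blood volume does not appear in this formula.

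**Reading A: input standardised to 1×10^6 cells.** Subset count = s × 1×10^6, with no term for c.

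| Mononuclear cells/µL | True CD4/µL | Bead CD4 count per tube |
|---|---|---|
| 200 | 0.20 × 200 = 40 | 0.20 × 1×10^6 = 200,000 |
| 1500 | 0.20 × 1500 = 300 | 0.20 × 1×10^6 = 200,000 |

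The true change is 300 ÷ 40 = 7.5-fold. The bead result is 1.0-fold.

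The input would not stay constant at the lowest counts. Yield = 12 mL × c × r.
- At 200/µL and 50% recovery: 12 × 0.2×10^6 × 0.5 = 1.2×10^6, so the target is met.
- At 100/µL and 50% recovery: 12 × 0.1×10^6 × 0.5 = 0.6×10^6, so it is missed.

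The second patient's tube would read 0.20 × 0.6×10^6 = 120,000. A true 20-fold rise from 100 to 2000/µL would then read as 200,000 ÷ 120,000 = 1.67-fold: strongly compressed, but not flat.

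**Reading B: the 1×10^6 is only an approximate yield, all recovered cells are counted, and the volume V is known.** Count ÷ V = s × c × r, so apparent fold change = true fold change × (r at visit 2 ÷ r at visit 1).
- Recovery 30% to 90%: the ratio runs from 0.3 ÷ 0.9 = 0.33 to 0.9 ÷ 0.3 = 3.0. A true 7.5-fold change reads as 2.5 to 22.5.
- Recovery 50% to 80%: the ratio runs from 0.5 ÷ 0.8 = 0.625 to 0.8 ÷ 0.5 = 1.6. A true 7.5-fold change reads as 4.7 to 12.0.

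The count follows the blood count here, but with an unmeasured error. V is not recorded either, which adds a further unknown.

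**Reading C: subset share × same-day clinical count.** 0.20 × 200 = 40/µL and 0.20 × 1500 = 300/µL. The blood count is recovered without V or r, provided losses fall about equally on the subsets so that the share is preserved.

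**The case against.** A reader might infer that the counts can never reflect the patient's blood and will hide immune recovery. The documents do not support that, for four reasons.

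- **The input may not be fixed.** The plan speaks of isolating about 1×10^6 cells. That can be a target, an approximate yield or a minimum for staining. The flat result needs a fixed input and a constant subset share. Under the other meanings the count still moves with the blood count, though with unknown error. Shifts in subset mix would show in any case.
- **The text conflicts with itself.** The whole-blood wording and the lysing step fit poorly with Ficoll-separated, frozen cells. If beads were added to a measured volume of fresh whole blood, the problem would not arise.
- **The description is a summary.** The sentence naming the flow method is broken in the available copy, and separation is deferred to a laboratory SOP that is not part of the documents. Volume and recovery may be handled there.
- **Immune recovery is not a named endpoint.** No result per microlitre of blood is claimed, and differentiation can be read from subset shares.

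All four points stand and limit the claim, but they do not remove it. On fresh blood, the processing list sends both flow tubes to separation and freezing and holds nothing back, and the Flow Cytometry subsection uses whole blood only as the source of the isolated cells that are then stained. On conversion, a clinical count could be paired later where one was done, but the plan does not say that it will be.

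**Conclusion.** The point holds in a limited form. Followed as written, Section 4.7.8 produces bead counts with no blood-volume denominator and no correction for separation or thaw losses, so they cannot be read as cells per microlitre of blood. This conclusion needs no assumed figure.

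The size of the distortion does rest on assumptions. It runs from a true 7.5-fold change reading as 1.0-fold (fixed input, constant 20% share) to an error of up to 3 times either way (known volume, recovery 30% to 90%), or 1.6 times (recovery 50% to 80%). Which case applies depends on what the 1×10^6 figure means, and the documents do not settle that.

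The consequence is confined to an exploratory laboratory measure. The primary feasibility hypothesis on training sessions and the sample size of 35 in Section 6.2 do not depend on it.

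**What to change.** 1. Reconcile the processing list with the Flow Cytometry subsection: state whether the material is fresh whole blood or thawed separated cells when the beads are added, whether the lysing step applies, and whether 1×10^6 is a target, a yield or a minimum.
2. From frozen cells, report subset percentages only, and name the parent population of each percentage.
3. Derive any absolute count as subset percentage × the same-day count of the same parent population (lymphocytes or mononuclear cells) from the clinical blood count with differential, abstracted from the chart. Alternatively, bead-count a measured aliquot of fresh heparin blood before the dilution step, and report it per microlitre of blood.

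**Cost.** The first route needs wording and one abstracted value per sample; Section 7.0 already provides for abstraction from the medical record into RedCap. Its drawbacks are that the result carries the error of two platforms, and that a visit without a same-day differential has no absolute count. The fresh-aliquot route avoids both, but needs the cytometer run while the blood is fresh, so these counts could not wait for the frozen samples.

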4.8 Safety endpoints

Treatment-related mortality (TRM) and grade 3-4 adverse events as defined by the National Cancer Institute Common Terminology Criteria for Adverse Events (NCI-CTCAE) ¹³⁵ will be monitored that are related to study interventions (e.g. exercising).

5.0 ANTICIPATED TOXICITIES

We do not anticipate any major toxicities occurring with participation in our investigation. The study interventions are evidenced-based and aimed at improving any health concerns the participants may have. To ensure the utmost safety of our participants going through exercise training (**as described above in section 4.1**) study staff will ensure that all patients who take beta-blockers will have taken their medication prior to training to avoid any blood pressure-related events.

6.0 STATISTICAL CONSIDERATIONS

General Considerations: All analyses will be summarized using appropriate effect estimates, confidence intervals, and p-values. All secondary and additional analyses will be evaluated at the standard 0.05 significance level. Descriptive statistics, including graphical displays, will be used to summarize all study variables. For continuous variables, means, standard deviations, percentiles, ranges, box plots and histograms will be generated. For categorical variables, frequencies and proportions will be generated. For time to event variables, event rates and survival curves will be generated. Statistical analyses will be performed using SAS for Windows (Version 9.3 or above: SAS Institute, Cary, NC) and the R statistical computing platform (R Core Team 2013; <http://www.R-project.org/>).

Categorical outcomes will be analyzed using chi-square techniques and logistic regression modeling. Length of stay outcomes will be analyzed using generalized linear models with appropriate link functions. Continuous, longitudinal outcomes such as the FACT-BMT and EQ-5D-5L will be analyzed using linear mixed regression modeling. Other continuous results (such as PG-SGA and numbers of days exercised and amount of exercise per day) will be analyzed using standard t-test approaches and correlated with outcomes. We will analyze TRM and CTCAE using Kaplan-Meier methods, log-rank tests, and Cox proportional hazard regression modeling.

6.1 Analysis of the Microbiota:

Shannon diversity index will be compared using unpaired two-sided Student's *t* tests with a more stringent cut-off of 0.0125 given multiple comparisons, by the Bonferroni correction for 4 time periods of independent comparisons. Comparisons of bacterial populations will be made by using the Adonis non-parametric method from within the Qiime package using Unifrac distance matrices from the populations being compared. P values will be calculated with $\alpha=0.05$. Metastats will be used for further statistical analyses of population structure, membership, and diversity with metadata such as time from transplant and dietary measurements such as caloric intake¹⁴⁵. Changes in specific bacterial families of interest will be compared using a two-sided Student's *t* test, with normality confirmed by D'Agostino and Pearson omnibus test with $p \leq 0.05$. All other comparisons will be done using two-sided Mann-Whitney tests. The R packages vegan¹⁴⁶, phyloseq¹⁴⁷, APE¹⁴⁸, randomForest¹⁴⁹, and arules¹⁵⁰ will be used for identification of associative patterns between taxa most associated with home care and hospital care recovery and other care and disease-related metadata. Comparisons will also be made between pairs of patients and caregivers to determine these effects.

6.2 Power and sample size calculations:

The primary hypothesis of interest for this safety and feasibility study is that at least 50% of enrolled patients will complete more than 50% of their high intensity interval training sessions. With a sample size of 35 patients, our study will be able to estimate a completion rate of 50% to within a 95% confidence interval of +/- 19%. For higher completion rates, such as 75%, we will be able to estimate to within a 95% confidence interval of +/- 17%¹⁵¹.

As noted in the exercise intervention section, in order to participate in the exercise intervention, subjects must first meet all inclusion and exclusion criteria and consent to participate, after which they will undergo cardiopulmonary exercise testing (CPET). CPET will be reviewed by a physician and subjects will not be able to participate in the intervention unless cleared by a physician. Therefore, not every patient who consents will participate in the intervention. Because our goal is to test the intervention in 30 patients, and assuming a 10% drop out rate (subjects who consent to participate but do not pass CPET testing), we will consent 35 subjects with the intent that 30 will participate in the intervention.

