1.0 OBJECTIVES

1.1 *Primary Objective:*

“To evaluate the feasibility and outcomes of a research pre-, peri-, and post-transplant optimization program (R-POP) to improve multiple domains of health including physical function, cognitive function, mental health, and diet and nutrition for patients planning to undergo or undergoing hematopoietic stem cell transplantation (HCT)”

1.2 *Secondary Objectives:*

1.2.1 Gather information on how the following parameters affect hematopoietic stem cell transplant patients’ outcomes and wellness/quality of life:

- physical function and activity,
- cognitive function,
- mental health,
- diet and nutrition,
- social support,
- caregiver support,
- microbiota diversity, and
- biomarkers of inflammation and frailty.

1.2.2 Compare additional clinical endpoints to include:

- overall survival,
- disease-free survival,
- rates of bacterial, fungal, and viral infections as well as overall infections,
- rates of hospital and intensive care unit admission/re-admission and length of stay,
- graft-versus-host disease
- transplant length of stay,
- return to work,
- falls,
- delirium,
- quality of life

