Risks to subjects are reasonable in that risks are low (e.g. related to exercise or psychological distress associated with questionnaire) and the goal of this study is to address these and other risks that may be raised. In fact, it is potentially beneficial to identify and address these risks prior to transplant than during the stress of transplant when they may emerge.

Importance of the Knowledge to be Gained

Importance of the knowledge to be gained

The success of this feasibility study would inform the development of a randomized phase 2 trial of pre-transplant interventions to improve transplant outcomes. This could establish a new standard of care for the treatment of transplant patients.

Why the risks to subjects are reasonable in relation to the importance of the knowledge that reasonably may be expected to result

Treatment-related mortality with allogeneic transplant ranges from 10-30%, with more frail individuals (i.e. functional impairment) at higher risk of adverse events. This study is low risk and has the potential to lead to new interventions to reduce treatment related mortality, which would have a significant impact on health.

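### Outside Shannon diversity, all secondary and additional analyses are judged at an unadjusted 0.05 with no ranking or exploratory label, although 32 patient instruments are measured both at new patient evaluation and at sign-off

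*Combined protocol and SAP*

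**What the plan says.** Section 6.0 (Statistical Considerations) opens with two general rules. The first attaches p-values to everything: "All analyses will be summarized using appropriate effect estimates, confidence intervals, and p-values". The second sets the threshold: "All secondary and additional analyses will be evaluated at the standard 0.05 significance level".

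Section 6.1 makes one exception. Shannon diversity is tested at a "more stringent cut-off of 0.0125 given multiple comparisons, by the Bonferroni correction for 4 time periods of independent comparisons". The comparison of bacterial populations returns to 0.05, and no adjustment is stated for the remaining microbiota tests ("All other comparisons will be done using two-sided Mann-Whitney tests").

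The primary hypothesis in section 6.2 lies outside this family. It concerns completion of training sessions and is sized by confidence-interval width: "The primary hypothesis of interest for this safety and feasibility study is that at least 50% of enrolled patients" complete more than half of their sessions.

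Secondary objective 1.2.1 is broad: "Gather information on how the following parameters affect hematopoietic stem cell transplant patients’ outcomes and wellness/quality of life", over eight listed areas. Objectives 1.2.2 and 1.2.3 add survival, infection, graft-versus-host disease, other clinical endpoints and caregiver quality of life. No key secondary endpoint or testing order is given for any of these. The word exploratory is applied only to one metabolomics assay in section 4.7.8.

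**The concern.** The 0.05 sentence is a positive instruction, not a gap. An analyst who follows it will call any secondary result below 0.05 significant, and nothing in the plan tells the reader to discount it for the number of results examined. The Bonferroni step for Shannon diversity shows that the authors accept the principle for four comparisons. The much larger set of patient instruments has no such protection.

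About 30 patients are expected to receive the intervention, in a single arm, so there is no control group against which to check a chance finding. Section 7.0 says where the results may lead: "The success of this feasibility study would inform the development of a randomized phase 2 trial of pre-transplant interventions to improve transplant outcomes". A domain that appears to change by chance could be reported as a finding and could influence what the next trial measures.

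**Working it through.** **The plan's own figure.** Shannon diversity: 0.05 / 4 = 0.0125, as stated. With four independent tests the familywise rate is 1 − (1 − 0.0125)^4 = 0.049. This is the only multiplicity figure in the plan.

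**Number of instruments.** Rows of the patient table in section 4.0 with both an NPE and a sign-off visit:

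| Domain | Count |
|---|---|
| Physical activity and function | 9 |
| Cognitive function | 5 |
| Mental health | 4 |
| Nutrition and diet (laboratory panel counted once) | 5 |
| Social support | 5 |
| Symptoms | 1 |
| Global | 3 |
| **Total** | **32** |

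Food security is left out because it has no sign-off visit, and HCT-CI because it is recorded at NPE only. Microbiota, biomarker, financial, activity-tracker and app rows are not counted. Several instruments yield more than one score (RBANS gives five index scores plus totals), and the delirium scale in section 4.2.4 is also scored at the six main timepoints. Taking 31 to 33 instruments instead of 32 moves the independent result only from 79.6% to 81.6%.

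**Assumptions, none of them stated in the plan.**
- One NPE-to-sign-off test per instrument. Section 6.0 does not name this contrast. Section 2.9 does ask whether patients can improve before transplant, and these are the two pre-transplant timepoints.
- Two-sided tests at 0.05, hence 0.025 in the direction of improvement. Section 6.0 does not state sidedness.
- No true change on any instrument.
- Normal test statistics with a common correlation ρ, varied because the documents give no value.

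**Formulas.** At ρ = 0:
- either direction: 1 − 0.95^32 = 0.806
- improvement only: 1 − 0.975^32 = 0.555

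At ρ > 0, with c = 1.96, X standard normal and Φ its distribution function, let a = (c − √ρ·X)/√(1 − ρ) and b = (−c − √ρ·X)/√(1 − ρ). The chance of at least one false positive is
- either direction: 1 − E{[Φ(a) − Φ(b)]^32}
- improvement only: 1 − E{Φ(a)^32}

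| ρ | Either direction | False improvement |
|---|---|---|
| 0 | 80.6% | 55.5% |
| 0.1 | 78.7% | 48.2% |
| 0.3 | 68.1% | 36.2% |
| 0.5 | 52.1% | 26.2% |
| 0.7 | 34.7% | 17.3% |
| 0.8 | 26.1% | 13.1% |

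The expected number of false positives does not depend on ρ: 32 × 0.05 = 1.6 in either direction and 32 × 0.025 = 0.8 improvements.

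**Correlation by domain (simulation).** With 0.3 within and 0.1 between domains, the chances are 76% in either direction and 46% for improvement. With 0.5 and 0.2 they are 68% and 38%.

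**With the adjustment.** Under the same null, the chance that any Benjamini-Hochberg adjusted value over 32 tests falls below 0.05 is, by simulation, 5.1%, 3.7% and 2.3% at ρ = 0, 0.5 and 0.8.

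**The case against.** The strongest reply is that this is a feasibility study. Its primary hypothesis is about session completion, objective 1.2.1 speaks of gathering information, and section 6.0 already requires effect estimates and confidence intervals. No secondary p-value is tied to a decision, and section 7.0 links the later trial to the success of this study, not to any particular test. Unadjusted secondary tests in such a setting are largely a labelling matter. That stands as far as it goes, and it is why the remedy is a labelling change. It does not remove the instruction to judge each result at 0.05, and the label is what the plan lacks.

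Four stronger readings are tempting, and the documents do not support them.
- A reader might infer that every secondary analysis is unadjusted. Section 6.1 adjusts Shannon diversity.
- A reader might infer that a false improvement is likely. Under the stated assumptions it exceeds 50% only when the tests are close to independent; it is 48% at correlation 0.1 and 26% at 0.5. Overlapping questionnaires in the same patients are probably correlated.
- A reader might multiply 32 instruments by five post-baseline visits and speak of 160 tests. Section 6.0 assigns continuous longitudinal outcomes to linear mixed models, not to visit-by-visit tests, and some instruments have fewer visits.
- A reader might express the familywise figures as a multiple of 0.05. Section 6.0 sets 0.05 per analysis and never promises a familywise rate.

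It is also fair to say that 1.2.1 treats the domains partly as predictors of outcome, so a set of 32 change tests is a construction. The primary objective does speak of improving several domains, which makes such tests plausible, but they remain an assumption.

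**Conclusion.** The point holds in a limited form. Except for Shannon diversity, section 6.0 judges secondary and additional analyses at an unadjusted 0.05, without a hierarchy or an exploratory label. With one NPE-to-sign-off test for each of 32 instruments and no true change, the chance of at least one false positive runs from 81% (independent) through 52% (correlation 0.5) to 26% (correlation 0.8). For a false improvement the figures are 56%, 26% and 13%.

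The sizes rest on a contrast that the plan does not name, on two-sided testing and on assumed correlations. The absence of a rule for reading these p-values rests on the text alone. A reader should not infer that a multiplicity adjustment would make the remaining results evidence for R-POP: in a single arm, real change from natural history or regression to the mean would survive any adjustment.

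**What to change.** In section 6.0, replace the sentence that sets 0.05 for secondary and additional analyses with:

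> Secondary and additional analyses are exploratory and are reported as estimates with 95% confidence intervals, without claims of statistical significance. Where p-values are shown for the NPE-to-sign-off changes, Benjamini-Hochberg adjusted values across all instruments are given beside the raw values. The Shannon diversity cut-off in 6.1 is unchanged.

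The clinical endpoints in 1.2.2 and the caregiver measures are covered by the first sentence and need no adjustment family of their own.

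The cost is a wording change and one extra column in the analysis tables; no new data, patients or visits are needed. The downside is that no secondary result can be called statistically significant, with Shannon diversity left under its own rule in 6.1.
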